6.8.1.6 SENSITIVITY ANALYSES

See “6.2.2 Sensitivity analyses for register data based outcomes”.

6.8.1.7 REPORTING AND STATISTICAL METHODS TO HANDLE MISSING DATA

On RWT-outcomes we expect *no missing data*, due to the nature of the Dream Register. Missing data will only be in case of a participant dying or moving out of Denmark. We consider these events to be so rare in our data that we will handle such missing data as *missing completely at random*. Thus, no imputation or other correction is necessary. We will report proportion of data missing.

We will report number of censored participants per treatment group.

6.8.2 PROPORTION IN ORDINARY WORK AT 12-MONTH FOLLOW-UP (SECONDARY OUTCOME) AND 24-MONTH FOLLOW-UP (EXPLORATORY OUTCOME) (OUTCOME #2 AND #14)

6.8.2.1 CALCULATION OF THE OUTCOME: SPECIFIC MEASUREMENT AND UNITS (AND TRANSFORMATION, WHERE APPLICABLE)

This outcome is calculated as the share of the treatment allocation group that on the time of follow-up was in stable RTW (≥ 4 weeks). Stable RTW if defined exactly as in the primary outcome, see 6.8.1.1.

6.8.2.2 SPECIFIC ANALYSIS METHOD AND RESULT PRESENTATION

Pairwise odds ratios will be calculated using logistic regression.

In addition to the presentation of odds ratios for tests at 12-month follow-up and 24-month follow-up, graphs are presented with the proportions in stable work at each week (week 1-52 for 12-month follow-up and week 1-104 for 24-month follow-up) for each of the three trial-arms. No statistical test will be performed for differences at week 1-51 or week 53-103. These curves are explorative, descriptive analyses.

6.8.2.3 COVARIATE ADJUSTMENT

Only for stratification variables, see 6.1 “Covariate adjustment in general”.

6.8.2.4 STATISTICAL METHOD ASSUMPTION CONTROL

The assumptions of the model are assumed to be acceptable, due to large sample, binary outcome, categorical independent variable.

6.8.2.5 ALTERNATIVE ANALYSIS METHOD IN CASE OF ASSUMPTION FAIL

No alternative methods are planned, since assumptions are assumed to hold.

6.8.2.6 SENSITIVITY ANALYSES

See “*6.2.2 Sensitivity analyses for register data based outcomes*”.

6.8.2.7 REPORTING AND STATISTICAL METHODS TO HANDLE MISSING DATA

Same as 6.8.1.7.

6.8.3 ALL SELF-REPORTED, NUMERICAL OUTCOMES, AT 6-, 12-, AND 24-MONTH FOLLOW-UP AT (SECONDARY OUTCOMES ##4-7 AND PREDEFINED EXPLORATORY OUTCOMES ##16-48)

6.8.3.1 CALCULATION OF THE OUTCOME: SPECIFIC MEASUREMENT AND UNITS (AND TRANSFORMATION, WHERE APPLICABLE)

All outcomes are calculated as the sum of scores on the respective measurement scales.

All 6-month follow-up outcome analyses are calculating using baseline and 6-month follow-up observations.

All 12-month follow-up outcome analyses are calculating using baseline and 6- and 12-month follow-up observations.

All 24-month follow-up outcome analyses are calculating using baseline and 6-, 12-, and 24-month follow-up observations.

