6.4 OUTCOME DEFINITIONS

The outcomes are reported as in the study design articles (except for selected outcomes, see alterations to SAP version 1 in appendix). The numbers 1 through 64 denotes the outcome numbers for reference purposes for this SAP section.

| PRIMARY AND SECONDARY OUTCOMES and outcome numbering | | | | | | |
|---|--------------------|--|--|--------------------------|---------------------------|---------------------------|
| Outcome class | Data source | Outcome | | 6-month follow-up | 12-month follow-up | 24-month follow-up |
| Primary | DREAM database | Time from baseline to RTW | | | 1 | |
| Secondary | DREAM database | Proportion in ordinary work | | | 2 | |
| | DREAM database | Time from baseline to RTW | | 3 | | 8 |
| | Questionnaire | Depressive symptoms measured by Beck Depression Inventory (BDI) ⁸ | | 4 | | |
| | Questionnaire | Anxiety symptoms measured by Beck Anxiety Inventory (BAI) ⁹ | | 5 | | |
| | Questionnaire | Stress symptoms measured by Cohen perceived stress scale (PSS) ¹⁰ | | 6 | | |
| | Questionnaire | Social and work related function measured by WSAS ¹¹ | | 7 | | |

| PREDEFINED EXPLORATORY OUTCOMES and outcome numbering | | | | | | |
|---|--------------------|--|---|-----------------|-----------------|----|
| Outcome class | Data source | Outcome | Follow-up | | | |
| | | | 6-month | 12-month | 24-month | |
| Pre-defined exploratory outcomes | DREAM database | Weeks in stable work (≥ 4 weeks) from baseline to current follow-up | | 9 | 10 | |
| | | Weeks in stable work (≥ 8 weeks) from baseline to current follow-up | | | 11 | |
| | | Weeks in stable work (≥ 12 weeks) from baseline to current follow-up | | | 12 | |
| | | Weeks in work from baseline to follow-up | | | 13 | |
| | | Proportion in ordinary work | | | 14 | |
| | | Number of recurrent sick leaves | | | 15 | |
| | Questionnaires | | Symptoms of Distress, anxiety, depression and somatization by Four-Dimensional Symptom Questionnaire (4DSQ) ¹² | 16 | 17 | 18 |
| | | | Depressive symptoms measured by Beck Depression Inventory (BDI) ⁹ | | 19 | 20 |
| | | | Anxiety symptoms measured by Beck Anxiety Inventory (BAI) ⁹ | | 21 | 22 |
| | | | Stress-symptoms measured by Cohen perceived stress scale (PSS) ¹⁰ | | 23 | 24 |
| | | | Social and work related function measured by WSAS ¹¹ | | 25 | 26 |
| | | | Burn-out symptoms measured by Karolinska Exhaustion Scale (KES) ¹³ | 27 | 28 | 29 |
| | | | Health-related quality of life measured by EQ-5D-5L ¹⁴ | 30 | 31 | 32 |

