6.6 OUTCOME BENEFIT DIRECTION

Referring to the hypothesis section, this table describes whether a “better outcome” is a higher or lower score on the numeric outcome variables.

| Outcome | Is “better outcome” defined by lower or higher numbers? | |
|---|---|----------------------|
| Time from baseline to RTW | Lower | |
| Proportion in stable work | | Higher |
| Time from baseline to RTW | Lower | |
| Weeks in work (all variations of stability definitions) | | Higher |
| Number of recurrent sick leaves | Lower ⁶ | |
| Depressive symptoms measured by Beck Depression Inventory (BDI) ⁸ | Lower | |
| Anxiety symptoms measured by Beck Anxiety Inventory (BAI) ⁹ | Lower | |
| Stress symptoms measured by Cohen perceived stress scale (PSS) ¹⁰ | Lower | |
| Social and work related function measured by WSAS ¹¹ | Lower | |
| Symptoms of Distress, anxiety, depression and somatization by Four-Dimensional Symptom Questionnaire (4DSQ) ¹² | Lower | |
| Burn-out symptoms measured by Karolinska Exhaustion Scale (KES) ¹³ | Lower | |
| Health-related quality of life measured by EQ-5D-5L ¹⁴ | | Higher ²¹ |
| General Quality of life scale measured by Flanagan's' QOLS ¹⁵ | | Higher |
| Self-efficacy concerning symptoms measured by IPQ subscale on personal control ¹⁶ | | Higher ²² |
| Return to work self-efficacy measured by RTW-SE ¹⁷ | | Higher |
| General self-efficacy measured by General Self-efficacy scale (GSS) ¹⁸ | | Higher |
| Client satisfaction with treatment measure measured by CSQ-8 ¹⁹ | | Higher |
| Presenteeism measured by Stanford Presenteeism Scale (SPS) ²⁰ | | Higher ²³ |

⁶ A low number of recurrent sick leave is a positive outcome only if duration of index sick leave is ideally balanced between compared groups.

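### SAP 6.8.3.1 scores every questionnaire as a plain sum, which is not reconciled with the EQ-5D-5L benefit direction in 6.6 and leaves the four 4DSQ dimensions, on the most direct reading, in one total

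*SAP*

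**What the plan says.** The heading of SAP 6.8.3 sets the scope: "SECONDARY OUTCOMES ##4-7 AND PREDEFINED EXPLORATORY OUTCOMES ##16-48". Under it, 6.8.3.1 gives the whole scoring rule in one sentence: "All outcomes are calculated as the sum of scores on the respective measurement scales". The subsection title allows for a transformation where one applies, but none is given.

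Two instruments in that scope matter here.

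- **EQ-5D-5L.** The outcome table in 6.4 numbers it #30, #31 and #32 for 6, 12 and 24 months. The direction table in 6.6 has the row "Health-related quality of life measured by EQ-5D-5L ¹⁴ | | Higher ²¹", so a higher value counts as better.
- **4DSQ.** The row in 6.4 is "Symptoms of Distress, anxiety, depression and somatization by Four-Dimensional Symptom Questionnaire (4DSQ) ¹² | 16 | 17 | 18": four constructs and one number per visit. In 6.6 it has a single direction entry, lower.

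Section 6.5 attaches three pairwise hypotheses to each outcome and refers to 6.6 for what a better outcome is. Section 6.8.3.2 reports pairwise differences in estimated marginal means with confidence intervals.

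**The concern.** Section 6.6 fixes how the sign of each group difference is read. If a score built by the rule in 6.8.3.1 runs the other way from its entry in 6.6, the arm with worse self-rated health is declared the better one. EQ-5D-5L is exposed to this, because its items grade problems and a plain sum of problem levels rises as health gets worse.

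For 4DSQ the issue is what can be learned. One total over distress, anxiety, depression and somatization cannot show which of them changed, and opposite movements offset each other. The same SAP serves a trial in anxiety and depression and a trial in stress disorders, so the dimension of most interest need not be the same in both.

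Timing adds some weight. SAP 3.5 says that all 24-month analyses are done unblinded. A choice left open between sum and index, or between total and dimension scores, could then be made for #18 and #32 with allocation known.

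**Working it through.** The SAP states no figure to reproduce here. The check compares 6.8.3.1 with 6.4 and 6.6 and adds simple arithmetic.

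**Scope.** #16-18 and #30-32 all lie within #16-48, so the sum rule covers both instruments.

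**EQ-5D-5L.** The SAP gives neither item coding nor a value set. Five items with five levels each is assumed, and the coding is varied:

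| Assumed coding | Best state | Worst state | Higher is better? | Agrees with 6.6? |
|---|---|---|---|---|
| 1 = no problems to 5 = worst | 5 × 1 = 5 | 5 × 5 = 25 | No | No |
| 5 = no problems to 1 = worst | 5 × 5 = 25 | 5 × 1 = 5 | Yes | Yes, but no recoding is stated |

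A third possibility is that a utility index is intended. The entry in 6.6 can then be right, but an index is not the sum that 6.8.3.1 prescribes, and no value set is named. The two sections therefore agree only through a step that the SAP does not state.

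Contrasts exposed under the first coding: 3 visits × 3 pairs = 9 per RCT.

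**4DSQ.** Outcome numbers listed: 3, one per visit, giving 3 × 3 pairs = 9 contrasts per RCT. If each dimension were its own outcome, there would be 4 dimensions × 3 visits = 12 outcomes and 12 × 3 = 36 contrasts. The list in 6.4 matches the first count and not the second.

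Illustration of offsetting in a total: a change of -3 in distress, +3 in somatization and 0 in the other two gives -3 + 3 + 0 + 0 = 0. The total shows no change although two dimensions moved.

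**The case against.** A reader might infer that the plan definitely reverses EQ-5D-5L. The document does not support that. The reversal depends on item coding that the SAP omits, and it disappears under reversed coding. The entry in 6.6 also carries a citation, so the intended direction is documented. A loosely written general sentence is a likelier explanation than an intention to read worse health as better. Because 6.8.3.2 reports estimates with intervals, a reader told the coding could recover the right interpretation. All of this stands, and it makes the EQ-5D-5L point conditional.

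A reader might equally infer that 4DSQ is certainly merged into one score. That is not proven either. The wording of 6.8.3.1 can mean a sum within each scale, 6.4 says that its numbers are for reference, no 4DSQ total is mentioned anywhere, and a single entry of lower would fit four scores. Against this, the SAP says subscale where it means one, as for the IPQ personal control measure, and three outcome numbers do not fit twelve outcomes. The total remains the more direct reading, but not the only one. How much a total would dilute any one dimension depends on subscale ranges that the SAP does not give, so no figure is offered.

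It is also true that the impact is limited. Both instruments are exploratory. BDI, BAI and PSS measure depression, anxiety and stress separately, as secondary outcomes at 6 months and exploratory ones at 12 and 24 months. Among the four 4DSQ constructs, only somatization has no other instrument in the outcome list.

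Finally, scoring details may stand in the study design articles, which 6.4 cites. That would excuse silence. It does not excuse a rule that 6.8.3.1 states without exception and that does not match 6.6.

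**Conclusion.** The point holds in conditional form and is worth correcting, though it does not touch the primary or any secondary outcome.

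- **EQ-5D-5L:** the sum rule is not reconciled with 6.6. With levels coded 1 = no problems to 5 = worst, all nine contrasts per RCT would be read with the wrong sign. With reversed coding none would. The SAP does not say which applies.
- **4DSQ:** on the most direct reading the outcome is one total that hides offsetting changes and cannot attribute an effect to a dimension. If four scores are meant, the outcome list in 6.4 is incomplete.

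The conclusion rests on the five-item, five-level structure assumed for EQ-5D-5L and on reading one outcome number as one score for 4DSQ.

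**What to change.** **In 6.8.3.1**, except both instruments from the sum rule:

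- EQ-5D-5L: analyse it as the utility index from a value set that the sponsor names, and leave 6.6 at higher. Alternatively, keep the level sum, state the coding (1 = no problems), and change 6.6 to lower.
- 4DSQ: analyse distress, anxiety, depression and somatization as four separate scores, each with lower as better.

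**In 6.4 and 6.6**, list the four 4DSQ scores so that the tables match the rule.

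**Cost.** Item data already collected are rescored. The 4DSQ contrasts rise from 9 to 36 per RCT, all exploratory, and the 98.3% intervals in 4.1 allow only for the three pairwise comparisons within an outcome, so the larger number should be acknowledged when results are read.

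SAP 1.2 says that the 6- and 12-month outcomes had been analysed before version 2. Any rescoring of #16, #17, #30 and #31 must therefore be labelled post hoc, and the scoring actually used at those visits must be reported. For #18 and #32, the choice should be recorded before the unblinded 24-month analysis.

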6.8.3.2 SPECIFIC ANALYSIS METHOD AND RESULT PRESENTATION

Linear mixed-effects model with unstructured covariance. Results will be presented in pairwise group differences between outcomes, from the estimated marginal means from the model, and the confidence intervals of these differences.

6.8.3.3 COVARIATE ADJUSTMENT

Only for stratification variables, see 6.1 “Covariate adjustment in general”.

6.8.3.4 STATISTICAL METHOD ASSUMPTION CONTROL

Assumption: normal distribution of scores. Control: Visual inspection by plotting the score residuals.

Assumption: normal distribution of individuals’ score differences between baseline and follow-up. Control: Visual inspection by plotting the score difference residuals.

Assumption: Equality and homogeneity of variance. Control: Breusch Pagan test and Bartlett’s test are used to identify violations of these assumptions.

6.8.3.5 ALTERNATIVE ANALYSIS METHOD IN CASE OF ASSUMPTION FAIL

In case of positive tests or visual inspections a robust variance estimator is used to correct standard errors.

6.8.3.6 SENSITIVITY ANALYSES

See “6.2.1 Sensitivity analyses for questionnaire based, self-reported data outcome”.

6.8.3.7 REPORTING AND STATISTICAL METHODS TO HANDLE MISSING DATA

Proportion and amount of missing data per outcome variable per follow-up event per treatment group will be reported.

To handle missing data, 100 multiple imputations will be performed, using following variables: stratification variables: diagnosis, municipality, employment status; age; gender; time to stable RTW; psychometric variables at baseline and all follow-up at outcome time: BDI, BAI, WSAS and PSS.

6.8.4 WEEKS OF WORK FROM BASELINE TO 12- AND 24-MONTH FOLLOW-UP (OUTCOMES ##10-14)

6.8.4.1 CALCULATION OF THE OUTCOME: SPECIFIC MEASUREMENT AND UNITS (AND TRANSFORMATION, WHERE APPLICABLE)

From baseline to follow-up, the number of weeks in work per participant is calculated. A week is noted as being in work, if no sick leave benefit has been received, *and* if a branch code is registered in the month of that week (branch codes are registered on monthly basis, if an individual has received salary from an ordinary job during that month).

For participants receiving flexible job benefit prior to randomization, and participants on sick leave from vacancy, the same principles apply, as described in 6.8.1.1, in the section “*Time to return to work-outcomes (outcomes #1, #3 and #8)*”.

At 24-month follow-up, this analysis is conducted with three variations each applying a different definition of return to work stability as sensitivity analyses. Whereas the first analysis uses the definition of stability from the primary outcome (minimum four weeks see section 6.8.1.1), these sensitivity analyses are conducted with a more conservative approach where stable return to work is defined as minimum 4, 8 and 12 weeks in work respectively.

6.8.4.2 SPECIFIC ANALYSIS METHOD AND RESULT PRESENTATION

Severely skewed data is expected for this outcome, why a robust Poisson regression model will be used to test the differences between groups.

6.8.4.3 COVARIATE ADJUSTMENT

Only for stratification variables, see 6.1 “*Covariate adjustment in general*”.

6.8.4.4 STATISTICAL METHOD ASSUMPTION CONTROL

Assumption: Poisson distribution. Control: X^2 goodness-of-fit test.

6.8.4.5 ALTERNATIVE ANALYSIS METHOD IN CASE OF ASSUMPTION FAIL

If X^2 goodness-of-fit test is significant, negative binomial regression model will be used instead. If X^2 goodness-of-fit test is significant for this distribution, zero inflated poisson regression will be used.

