4 STATISTICAL PRINCIPLES

4.1 CONFIDENCE INTERVALS AND P-VALUES

For all outcomes, the three randomization groups are pairwise compared. Due to these multiple comparisons, we will calculate 98,3% confidence intervals, according to Bonferroni correction of desired α -level of 0,05 in testing of 3 hypotheses:

$$\alpha\text{-level: } 0,05 \times \frac{1}{3} \cong 0,0167 \Rightarrow \text{Confidence Interval: } 1 - 0,0167 \cong 98,33\%$$

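### Weeks in work: the goodness-of-fit ladder always discards robust Poisson, for models whose error rates as written are badly wrong

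*SAP*

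**What the plan says.** SAP 6.8.4.1 defines the outcome: "From baseline to follow-up, the number of weeks in work per participant is calculated". The windows given in 6.8.2.2 ("week 1-52 for 12-month follow-up and week 1-104 for 24-month follow-up") bound it at 52 and 104 weeks.

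The model is set in 6.8.4.2: "Severely skewed data is expected for this outcome, why a robust Poisson regression model will be used to test the differences between groups". Section 6.8.4.4 then lists an assumption and a check: "Assumption: Poisson distribution. Control: X^2 goodness-of-fit test". Section 6.8.4.5 acts on that check. If the "goodness-of-fit test is significant, negative binomial regression model will be used instead". If the test "is significant for this distribution, zero inflated poisson regression will be used".

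Neither fallback is given a robust variance, although 6.8.3.5 states one explicitly for the questionnaire outcomes. The SAP does not say which chi-square test is meant, or which part of the zero-inflated model gives the group comparison. For the test level, 4.1 states: "we will calculate 98,3% confidence intervals, according to Bonferroni correction".

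The outcomes concerned are #9-13 in the table in 6.4. (The heading of 6.8.4 numbers them 10-14, but #14 is a proportion and is handled in 6.8.2.)

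**The concern.** Robust Poisson regression needs the model for the mean to be right. It does not need the counts to be Poisson, because the sandwich standard error takes the spread from the data. A Poisson goodness-of-fit test is therefore not a check of this method, and the skew given as the reason for choosing the method is what makes the test fail.

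The two replacements fail in opposite directions:

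- **Negative binomial.** It has to explain the pile of zeros by a very large dispersion, which implies a long upper tail that a bounded outcome cannot have. Its standard error is too large.
- **Zero-inflated Poisson.** It takes the zeros out and assumes pure Poisson spread among those with some work. Its standard error is far too small. It also splits the arm effect into two coefficients, neither of which compares mean weeks over all randomized participants.

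Depending on where the ladder stops, a real difference is likely to be missed or a chance one reported. The 24-month weeks-in-work outcomes all pass through it. These include the three stability thresholds (#10-12) described in SAP 1.2 and the pre-planned #13.

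**Working it through.** **Inputs from the SAP.** 198 per group (153 at power 0.8), 210 days (30 weeks) to return to work in controls, hazard ratio 1.5 and α = 0.05/3 = 0.0167 (3.3 and 4.1), taken as two-sided, so z = 2.394. Windows are 52 and 104 weeks.

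**The plan's own figure.** Exponential return to work, accrual over 730 days and 365 days of further follow-up, with 210 days read as a median and 315 days in the other group, give 197.7 and 153.3 per group. These match 198 and 153. (With 140 days in the other group the results are 178.6 and 138.4.) The exponential with median 30 weeks is therefore used below.

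**Assumptions not in the SAP, so varied.** Share never returning, 0% or 20%; relapse, none or a mean work spell of 52 weeks.

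**Step 1: must the Poisson test reject?** Take the mildest case, with everyone eventually returning and no relapse.
- Share with zero weeks at week 52: 2^(-52/30) = 0.30, or about 179 of 594.
- Mean weeks: 52 - (30/ln 2)(1 - 0.30) = 21.7.
- A Poisson variable with mean 21.7 is zero with probability e^(-21.7), below one in a billion.
- With about 590 degrees of freedom, a 5% Pearson test rejects once variance/mean exceeds about 1 + 1.645√(2/590) = 1.10. Simulated values were 13-29.

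**Step 2: why the fallback standard errors are wrong.** Same case, simulated values: mean 21.7, variance/mean 16.1, zeros 31%, negative binomial dispersion 2.45.
- Actual standard error of the log ratio of means: √[(2/198)(16.1/21.7)] = 0.087.
- Negative binomial: √[(2/198)(1/21.7 + 2.45)] = 0.159. Under the null this needs |Z| > 2.394 × 0.159/0.087 ≈ 4.4, a probability near 0.00001.
- Zero-inflated count part: √[2/(198 × 21.7)] = 0.022. Among the 69% with some work (137 per arm), the mean is 21.7/0.69 = 31.4 and the variance (16.1 × 21.7 + 21.7²)/0.69 - 31.4² ≈ 200. The actual standard error is √[2 × 200/(31.4² × 137)] = 0.054. Rejection needs only |Z| > 2.394 × 0.022/0.054 ≈ 0.95, a probability of about 34%.

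**Step 3: simulation.** 1000 replicates per scenario, two arms, model-based standard errors for the fallbacks, stratification covariates omitted. RP = robust Poisson, NB = negative binomial, ZIP = zero-inflated Poisson count part. 198 per arm.

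| Weeks | Never return | Relapse | Zeros | Var/mean | False positives RP / NB / ZIP | Power RP v NB |
|---|---|---|---|---|---|---|
| 52 | 0% | none | 31% | 16.1 | 1.4% / 0% / 36.3% | 0.82 v 0.18 |
| 52 | 20% | yes | 45% | 19.1 | 1.7% / 0% / 42.9% | 0.53 v 0.06 |
| 104 | 20% | none | 27% | 29.1 | 1.4% / 0% / 42.2% | 0.49 v 0.002 |
| 104 | 0% | yes | 9% | 19.0 | 1.5% / 0.1% / 52.4% | 0.94 v 0.67 |
| 104 | 20% | yes | 27% | 27.7 | 2.2% / 0% / 54.3% | 0.62 v 0.06 |

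In the remaining scenario (104 weeks, all eventually return, no relapse), power was 0.93 v 0.42. With 153 per arm in the last row's scenario, false positives were 1.8% / 0.1% / 54.9%. The Poisson fit was rejected in 100% of replicates in every scenario.

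A separate simulation with 12% never returning and 30% losing part of later work time gave false positives of about 1-3%, 0-0.2% and 36-58%, and power of 48-49% v 3-4%.

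**Step 4: where does the ladder stop?** It depends on the unspecified second test.
- Upper-tail Pearson: never rejects the negative binomial (Pearson/df 0.22-0.51), so the analysis stays there.
- Observed against expected frequencies: rejects in 100%, so it moves to zero-inflated Poisson.
- Deviance: rejects in 93-100% of replicates in most scenarios, but in 0-1% in the 52-week scenario with 20% never returning.

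**The case against.** The strongest reply is that the error rates belong to the variance estimator rather than to the models. SAP 6.8.4.5 is silent on variance, and with robust variance both fallbacks hold their level (negative binomial 1.4-2.2%, zero-inflated count part 1.6-2.3%). This is correct, and the error rates above are conditional on model-based standard errors. That is the literal reading, because the word robust is attached only to Poisson here and is spelled out in 6.8.3.5 where it is wanted. Robust variance would not settle which zero-inflated coefficient is the result.

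Second, a Pearson test is a natural reading of the check, and under it zero-inflated Poisson is never reached. The error is then only conservative, and since the negative binomial with a log link also models a ratio of means, the change of estimand does not arise. This stands, but the SAP does not name the test, and 3.5 says the 24-month analyses are unblinded, so the choice would be made with allocation known.

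Third, the size of the power loss depends on assumed never-return and relapse rates and is moderate in the mildest scenario (0.94 v 0.67). This also stands; hence the range.

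Fourth, #9-13 are exploratory, 6.2.2 makes #9-12 sensitivity analyses of #13, and 6.2 says sensitivity results do not replace main results. That limits the importance but does not make the rule sound.

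**Conclusion.** The concern holds. The gate tests a property that the chosen method does not need and that these data cannot have, so the analysis named in 6.8.4.2 would in practice never be the one reported. As written, its replacement either almost never rejects (0-0.1% at a nominal 1.67%, with power cut to between 0.002 and 0.67) or rejects a true null in 36-55% of trials. Robust Poisson kept throughout holds 1.4-2.2%, with power of 0.49-0.94.

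These figures rest on exponential return with median 30 weeks, the assumed never-return and relapse rates, model-based standard errors in the fallbacks and no stratification covariates. Certain rejection of the Poisson fit does not depend on the never-return or relapse assumptions; Step 1 shows it without them. The primary and secondary outcomes are unaffected, so this should be corrected but does not threaten the trial's main conclusion.

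**What to change.** Delete 6.8.4.4 and 6.8.4.5. State in 6.8.4.2 that Poisson regression with robust (sandwich) standard errors, adjusted for the stratification variables, is the only test for weeks in work whatever the fit. The result is the ratio of mean weeks for each pairwise comparison with its 98.3% confidence interval. A difference in mean weeks with a bootstrap interval can be added for readability.

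The cost is SAP wording, and there is less analysis to run. Because SAP 1.2 says the 12-month outcomes have already been analysed, the change needs a dated note that it follows those results. Analysing #9 by the same rule would keep the 12- and 24-month results comparable.
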